4.4 Schedule of Treatment for each visit

Procedure	Number of interventions	Routine	Average time	Who will conduct	Place
PHASE 1					
Consent for CVI	1	no	5 mins	researcher	Electronic
Content validity index	1	0	10 mins	researcher	Electronic
Consent for cognitive interview	1	0	5 mins	researcher	Electronic
Cognitive interviews	1	0	1 hour	researcher	Virtual (video call)
Consent for construct validity testing	1	0	5 mins	researcher	Electronic
Construct validity testing	1	0	10 mins	researcher	Electronic
Consent (+ reading PIS) for service users – PHASE 1	1	0	15 mins – as long as the participant needs	Researchers or nurses	Virtual/GP surgery
ADRe Profile self-completion	1	1	10 – 25 mins	service users	Virtual
ADRe Profile completion with nurse	1	1	10 – 25 mins	Nurse-researchers	Virtual/GP surgery

SU Non CTIMP Healthcare Research Protocol

researcher					
Debrief	1	0	15 mins	researchers	Virtual/GP surgery
PHASE 2					
Consent (+ reading PIS)	1	0	15 mins – as long as the participant needs	Researchers or nurses	Virtual/GP surgery/patient's home
Introductory training for nurses	1	0	15 mins	Researcher	Virtual/GP surgery
ADRe Profile self-completion	2	1	10 – 25 mins	service users	electronically or by post
ADRe Profile completion with a nurse/nurse-researcher	2	1	10 – 25 mins	nurse/researchers	Virtual/GP surgery/patient's home
Debrief	1	0	15 mins	researchers	Virtual/GP surgery/patient's home
PHASE 3					
Survey – service users	1	0	10 mins	researchers	Electronic/by post
Survey – GP's	1	0	10 mins	researchers	Electronic/by post
Survey - pharmacists	1	0	10 mins	researchers	Electronic/by post
Survey – nurses/care assistants	1	0	10 mins	researchers	Electronic/by post
Interview -	1	0	1 hour	researchers	Virtual/GP surgery/patient's

SU Non CTIMP Healthcare Research Protocol

service users					home
Interview – GP's	1	0	1 hour	researchers	Virtual/GP surgery
Interview - pharmacists	1	0	1 hour	researchers	Virtual/GP surgery
Interview – nurses/care assistants	1	0	1 hour	researchers	Virtual/GP surgery
Debrief /feedback	1	1	10 mins	researcher	Virtual/GP surgery

4.5 Schedule of Assessment (in Diagrammatic Format)

Phase of study	Intervention arm	Control arm
Phase 1 - feasibility	Medical notes accessed for items to populate ADRe Profile	No control
	Self-completed ADRe Profile	
	Researcher-completed ADRe Profile	
Phase 2 – RCT step 1	Medical notes accessed for items to populate ADRe Profile	Medical notes accessed for items to populate ADRe Profile
	Self-completed ADRe Profile	Standard of care
	Nurse or researcher-completed ADRe Profile	Standard of care
Phase 2 – RCT step 2	Medical notes accessed for items to populate ADRe Profile	Medical notes accessed for items to populate ADRe Profile
	Self-completed ADRe Profile	Standard of care
	Researcher-completed ADRe Profile	Standard of care
Phase 3 – Survey and interviews	Survey administered to service user participants	
	Interviews performed with selected	

	participants (3 service users, 3 nurses, 3 GP's, 3 pharmacists)	
--	---	--

4.6 Follow up Procedures (if applicable)

N/A

4.7 Laboratory Assessments (if applicable)

N/A

4.8 Radiology Assessments (if applicable)

N/A

4.9 Medical Devices (if applicable)

ADRe Profile is designed to help healthcare professionals detect possible adverse side effects caused by service users' primary care medicines, and review their general health and well-being, in case this has worsened as a result of these medicines. It brings together relevant information and gives the prescriber or pharmacist reviewer a picture of all possible adverse effects and all medicines prescribed.

4.9 End of Study Definition

End of a clinical trial will be the last visit (or virtual visit) of the last subject to complete the ADRe Profile. End of the whole study will be the interview with the last interviewee. The end of the study is estimated to be October 2022 and no later than July 2023.

Criteria for stopping the study early:

- inability to access GP service users, recruit participating GP practices
- serious event precluding principle or chief investigator from finishing the research
- results from phase 1 show no justification for continuing with phase 2, results from phase 2 show no justification for continuing with phase 3.

Once the end of study has been declared, no further substantial amendments will be made and a Clinical Trial Summary Report will be produced. The HRA ethics committee (The 'Declaration of the End of Trial Form' will be completed) and the NHS R&D offices will also be notified within 3 months of the end of the study.

4.11 Procedures for unblinding (if applicable)

N/A

SU Non CTIMP Healthcare Research Protocol

4.12 Subject Withdrawal

Criteria for participant withdrawal:

- participant's /consultee's wishes
- physical deterioration, where continuing with the research would represent a burden on the participant
- failure to engage in participation
- move into long-term care facilities
- prolonged hospitalisation

4.13 Data Collection and Follow up for Withdrawn Subjects

Unless requested otherwise, data that has been already collected will be kept for withdrawn participants.

5. Laboratories (if applicable)

N/A

6. Safety Reporting

6.1 General Definitions

Adverse Event (AE)

An AE is any untoward medical occurrence in a subject to whom a medicinal product has been administered, including occurrences which are not necessarily caused by or related to that product. An AE can therefore be any unfavourable and unintended sign (including an abnormal laboratory finding), symptom or disease temporarily associated with study activities.

Serious Adverse Event (SAE)

An SAE fulfils at least one of the following criteria:

- Is fatal – results in death (NOTE: death is an outcome, not an event)
- Is life-threatening
- Requires inpatient hospitalisation or prolongation of existing hospitalisation
- Results in persistent or significant disability/incapacity
- Is a congenital anomaly/birth defect
- Is otherwise considered medically significant by the Investigator

6.1.1 Adverse Event (AE)

If an adverse event is identified or reported, it will be recorded in the participant's medical records. Any adverse events will be assessed by the clinical team and the chief investigator. Any adverse events arising as a result of the ADRe checklist will be passed to the sponsor's representative and the participant's responsible clinician for assessment. No adverse events have arisen as a result of using the ADRe

SU Non CTIMP Healthcare Research Protocol

checklists in 2 trials and 3 observation studies. Previous research has not identified any harm resulting from completing the ADRe Profile checklist. We are not planning on establishing a Data Monitoring Committee.

6.1.2 Serious Adverse Event (SAE)

Previous research has not identified any harm resulting from completing the ADRe Profile checklist. We are not planning on establishing a Data Monitoring Committee.

6.2 Investigators Assessment

6.2.1 Seriousness

The Chief/Principal Investigator or the clinical team responsible for the care of the patient will assess whether the event is serious.

6.2.2 Causality

The Chief Investigator will be responsible for assessing the causality.

6.2.3 Expectedness

It is unlikely that completing a checklist should cause any serious adverse events.

6.2.4 Severity

The Chief Investigator will assess the severity of the event according to the following definitions:

Mild: Some discomfort noted but without disruption of daily life

Moderate: Discomfort enough to affect/reduce normal activity

Severe: Complete inability to perform daily activities and lead a normal life

6.3 Notification and reporting Adverse Events or Reactions

Any Adverse Event will be recorded in the study file and the participant will be followed up by the research team. The Adverse Event will be documented in the participant's medical notes and the CRF.

6.4 Notification and Reporting of Serious Adverse Events

6.4.1

Related and unexpected Serious Adverse Events will be reported to the sponsor within 24 hours of learning of the event and to the Main REC within 15 days.

6.5 Urgent Safety Measures

SU Non CTIMP Healthcare Research Protocol

Should the Chief Investigator need to take any urgent safety measures to ensure the safety and protection of the trial participants from any immediate hazard to their health and safety, any such measures will be taken immediately. The Sponsor and the Main Ethics Committee will be informed immediately via telephone and in writing within 3 days (in a form of a substantial amendment). The Sponsor will be sent a copy of all correspondence.

6.6 Annual Safety Reporting

The Chief Investigator will send the Annual Progress Report to the main REC (using NRES template).

6.7 Procedures for reporting blinded 'unexpected' and related' SAEs

N/A

6.8 Overview of the Safety Reporting Process/Pharmacovigilance responsibilities

It is extremely unlikely that the implementation of the ADRe Profile (checklist) should cause any harm. The ADRe Profile has been developed to identify and support amelioration of potential side effects from commonly prescribed medicines. As part of the study protocol, the completed ADRe Profile and the list of patient's medicines is reviewed by the study pharmacist and, if needed, the patient's GP.

7. Statistical Considerations

7.1 Primary Endpoint Efficacy Analysis

Differences between before and after the intervention will be calculated for: problems addressed, prescription regimens, NHS use, and compared, adjusting for site. The impact of age, diagnoses, and medicines' use (numbers and types of medicines prescribed) will be accounted.

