Data will be entered into excel via the electronic version of ADRe, imported into SPSS and described for the before and after ADRe administrations. Statistical analysis: differences between before and after the intervention will be calculated for: number and nature of problems addressed, prescription regimens, and NHS use. The impact of GP practice, age, diagnoses, and medicines' use (numbers and types of medicines prescribed) will be described and accounted for in exploratory bivariate and multivariate regression analyses. To explore the recorded changes and potential for further clinical gains, putative aetiologies of service users' signs and symptoms will be ascribed, using clinical information from medical and nursing records, including, but not restricted to, information on ADRe, and the list of medications prescribed (and over the counter). The ascription will be checked by supervisors using manufacturers' literature and formularies. Juxtaposition of ADRe and medication lists will generate suggestions for changes to improve the processes and possibly the outcomes of care. The prevalence of problems on the before and after profiles will be compared with two by two contingency tables, using McNemar's test for related dichotomous variables (Altman 1991).

Survey

Data will be described using the Statistical Package for Social Sciences (SPSS) and later combined with the interview results.

Interviews and recorded ADRe consultations

All interviews (and relevant parts of ADRe consultations) will be transcribed verbatim by the researcher/professional transcriber and anonymised. Transcripts will be

SU Non CTIMP Healthcare Research Protocol

coded, categorised, analysed and interpreted alongside the data of all completed cases, to identify, analyse and report patterns within data (Braun and Clark, 2006). The transcripts will be analysed by the team using the constant comparative method which will provide a systematic, re-iterative way of comparing and contrasting emerging codes, categories and concepts and ensure that theoretical perspectives are embedded in the description of change. Two researchers ([name]) will ensure validity of the analysis and verify interpretation. Disagreements will be resolved through discussion at team meetings. Diaries/logs will also be analysed in association with interview transcripts.

Triangulation

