8.3 Case Report Form

Swansea Trials Unit's forms will be adapted for use in CRF (with permission)

1 List of ADReGP Case Report Forms

Number	Title
FORM 01	Inclusion Criteria
FORM 02	Exclusion Criteria
FORM 03	Eligibility review
FORM 04	Randomisation/Enrolment
FORM 05	Patient Details (age and gender)
FORM 06	Baseline Medical Conditions
FORM 07	Baseline Medication list
FORM 08	Baseline ADRe Profile from available medical notes
FORM 09	Baseline Self-completed ADRe Profile
FORM 10	Baseline Nurse/researcher-completed ADRe Profile
FORM 11	Endpoint Medical Conditions
FORM 12	Endpoint Medication list
FORM 13	Endpoint ADRe Profile from available medical notes
FORM 14	Endpoint Self-completed ADRe Profile
FORM 15	Endpoint Nurse/researcher-completed ADRe Profile
FORM 16	Adverse Events
FORM 17	Serious Adverse Events
FORM 18	End of Treatment
FORM 19	Details of Death
FORM 20	Consent Withdrawal
FORM 21	PI Declaration
QUESTIONNAIRES	Patient survey Nurse survey GP survey Pharmacist survey

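### Before/after differences are compared without the patient's baseline value as a covariate, which costs precision and leaves the result exposed to chance imbalance between 3 and 3 practices

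*Combined protocol and SAP*

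**What the plan says.** Section 7.1, the only efficacy section with content (7.2 is marked not applicable), reads: "Differences between before and after the intervention will be calculated for: problems addressed, prescription regimens, NHS use, and compared, adjusting for site". It continues: "The impact of age, diagnoses, and medicines' use (numbers and types of medicines prescribed) will be accounted". I take the comparison to be between arms.

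Section 7.5 repeats the approach: "differences between before and after the intervention will be calculated for: number and nature of problems addressed, prescription regimens, and NHS use". There, GP practice, age, diagnoses and medicines' use are to be "accounted for in exploratory bivariate and multivariate regression analyses". Section 7.5 also compares the prevalence of problems before and after, "using McNemar's test for related dichotomous variables". That test is paired within patient and has no arm term.

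The baseline data are set out elsewhere:

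- **Section 4.5.** The row "Medical notes accessed for items to populate ADRe Profile" appears in both the intervention and the control column at RCT steps 1 and 2. Self-completed and nurse- or researcher-completed profiles appear in the intervention column only; controls have standard of care.
- **Section 8.3.** Form 08 is "Baseline ADRe Profile from available medical notes", with endpoint counterpart Form 13. Form 07 is "Baseline Medication list", with endpoint counterpart Form 12. No form is listed for NHS use.

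The Phase 2 primary endpoints in section 2.1 are problems newly identified and problems addressed, patients with a change in signs and symptoms, and patients whose prescription regimen changes in drug or dose.

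**The concern.** A simple before/after difference fixes the slope on baseline at 1. Counts of problems or contacts usually correlate less than perfectly over time, so patients who start high tend to fall back towards the average whatever their arm. A difference score passes that fall on to the treatment comparison: the arm that happens to start higher appears to improve more. Estimating the slope from the data removes this dependence and reduces the variance.

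This matters more here than in a large individually randomised trial. Six practices are randomised whole, so noticeable baseline differences between arms will be common. If site means practice, adjusting for it does not help, because every practice lies wholly within one arm. The listed covariates include the number of medicines, which partly covers the prescription outcome, but not the baseline number of problems or prior NHS use.

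**Working it through.** **Inputs from the documents.** 6 practices of 10 patients, 20% loss, ICC 0.02, design effect 1.18, and proportions improved of 17/19 and 9/19 (section 7.4). Randomisation is by practice (section 2.2). The 30 intervention patients at 10 per practice give 3 practices per arm.

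**Inputs assumed.** The documents give no SD and no before-after correlation r for any RCT outcome. I take r from 0.3 to 0.7, with equal variances before and after and a roughly continuous outcome.

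**1. The plan's own figure.** Two proportions, 17/19 v 9/19, two-sided 5%, 90% power, unpooled variance: 20.4, so 21 per arm (42 against the stated 40). Design effect 1 + 9 × 0.02 = 1.18; 40 × 1.18 = 47.2, taken as 48; 48/0.8 = 60. The chain reproduces to within 2 patients, although the pooled two-sided formula gives 24 per arm. It rests on a binary outcome and uses no baseline value, so it says nothing for or against baseline adjustment of the counts.

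**2. Precision.** In units of the outcome variance, the change score has variance 2(1-r) and the baseline-adjusted comparison 1-r². The ratio is (1-r²)/(2(1-r)) = (1+r)/2.

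| r | change, 2(1-r) | adjusted, 1-r² | ratio | 48 patients on change scores are worth |
|---|---|---|---|---|
| 0.3 | 1.40 | 0.91 | 0.65 | 31 |
| 0.5 | 1.00 | 0.75 | 0.75 | 36 |
| 0.7 | 0.60 | 0.51 | 0.85 | 41 |

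Below r = 0.5 the change score has variance above 1, so it is less precise than ignoring baseline altogether.

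Simulation of 20,000 trials per r (6 practices of 8, ICC 0.02, no effect) gave SDs of the estimate, change v adjusted, of 0.367 v 0.298, 0.312 v 0.274 and 0.238 v 0.221. Mean change-score estimates were 0.005, 0.001 and -0.002, so there is no bias on average.

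**3. Chance imbalance.** The variance of the baseline difference between arms is 2(1+(m-1) × 0.02)/(3m).

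- m = 10: 2 × 1.18/30 = 0.0787, SD 0.28.
- m = 8: 2 × 1.14/24 = 0.095, SD 0.31, 95% range ±0.60.

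For a given imbalance the change-score result moves by (1-r) times it. At 0.31 SD that is 0.22, 0.15 and 0.09 SD for r = 0.3, 0.5 and 0.7. At 0.60 SD it is 0.42, 0.30 and 0.18. In the simulation the adjusted estimate did not depend on the imbalance.

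**4. Power, as illustration only.** For an effect of 0.8 SD, which the documents do not give, and a practice-level t-test on 4 degrees of freedom with 8 per practice, simulated power rises from 39% to 54%, 51% to 61% and 71% to 77% at r = 0.3, 0.5 and 0.7. At r = 0.85 it is 94% v 95%.

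**5. The binary outcome.** The ratio in step 2 does not apply to improvement in at least 1 problem, but that outcome does depend on the number of problems at the start. If each problem had a 20% chance of improving (assumed), the probability is 1-0.8² = 36% for a patient with 2 problems and 1-0.8⁴ = 59% with 4. Those are single patients. Between arms the contrast is smaller: with a mean of 3 problems and an SD of 2 (both assumed), a 0.28 SD imbalance is 0.56 problems, giving 1-0.8^3 = 49% v 1-0.8^3.56 = 55%.

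**6. Adjusting the difference itself.** In a linear model, follow-up = a + τ·arm + β·baseline is the same as difference = a + τ·arm + (β-1)·baseline. The arm effect τ is identical, so the plan can keep its differences as the outcome and add the baseline term.

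**The case against.** The strongest reply is that nothing here is wrong, only less efficient. Randomisation makes the change score valid, the simulated mean is at zero, and the type I error is about 5%. That stands. A reader might infer that the planned analysis biases the trial. The documents do not support that: the shift in step 3 is conditional on the imbalance that happens to occur and averages out over randomisations.

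A second tempting inference is that every outcome already has its baseline collected in both arms. That holds for the notes-based profile, and the CRF list supports it for medicines. It does not hold for self-completed or nurse-completed profiles, and it is not documented for NHS use, which has neither a form nor a look-back period.

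A third is that Form 13 should simply be regressed on Form 08, and Form 12 on Form 07. That would replace the declared endpoints. Section 1.3 reports that detected problems rose from 2 to 9 with the Profile in an earlier study, so a model for total recorded problems could read better detection as more problems. The same section reports fewer mental health prescriptions with no change in total medicines, so a medicine count could miss real regimen changes.

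It is also fair to say that the outcomes are counts and binary changes, not normal scores with equal variances, that the gain shrinks as r rises, and that the exploratory regressions of 7.5 do not exclude a baseline term. The first two limit how far the figures can be trusted. The third is a reason to name the term in advance, not to leave it open.

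**Conclusion.** The point holds as a matter of precision. Sections 7.1 and 7.5 compare differences and name no baseline-outcome covariate, although a like-for-like notes-based baseline is scheduled in both arms. For count outcomes the change score is less precise at any r below 1: the adjusted variance is 0.65 to 0.85 of it for r of 0.3 to 0.7, assuming roughly continuous outcomes with equal variances. With six practices a chance baseline difference has an SD of about 0.28 to 0.31 patient SD and carries into the result by a factor of (1-r). The absence of the covariate can be read directly from the documents. The size of the loss cannot be, because r is not given. In a trial with 48 expected completers this is worth changing, but it does not invalidate the planned analysis.

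**What to change.** Keep the section 2.1 endpoints as they are. In 7.1 and 7.5, add a patient-level baseline covariate to the between-arm comparison:

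- **Number of problems addressed:** the before value of the same count, taken from the notes in both arms.
- **At least 1 problem improved:** the baseline number of notes-recorded problems (Form 08), in a model suited to a binary outcome.
- **Prescription changes:** state that the number of medicines already listed as a covariate is the baseline value from Form 07.
- **NHS use:** adjust only if contacts in a comparable pre-period are extracted from the notes; if so, define the period and add a form.

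Fit the covariate at patient level within an analysis that respects practice clustering, for example as the first stage of a two-stage cluster analysis, so that it uses none of the roughly 4 practice-level degrees of freedom. Site fixed effects cannot be fitted together with arm (6 site terms plus arm give 7 columns of rank 6), so the wording on site should be settled in the same edit. Keep raw before/after differences as description, and do not replace the problem or prescription endpoints with total problem or medicine counts.

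For problems and prescriptions the cost is analysis wording, using forms already listed. For NHS use it is a small additional extraction from the notes.

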7.2 Secondary Endpoint Efficacy Analysis

N/A

7.3 Safety Endpoints

N/A

7.4 Sample Size

RCT (sample = 60): Previously, in a 'before and after' single arm intervention study, with participants acting as their own controls, 17/19 (89%) had improvement in at least 1 clinical problem when ADRe Profiles for polypharmacy were used (Jordan et

SU Non CTIMP Healthcare Research Protocol
al submitted). We hypothesised that 9/19 (47%) would have shown some improvement without intervention, necessitating an effective sample of 40 patients (20 in each arm), with 5% significance and 90% power (Uitenbroek 1997). Based on the reported intra-cluster coefficient (0.02), (Jordan et al 2015), and a design effect of 1.18, to achieve an effective sample size of 40, we need an actual sample size of 48 (Killip et al 2004). 10 patients in each of 6 clusters (GP practices) allows for 20% loss to follow up, which is realistic in general practice, where either patient or nurse may be unavailable for follow up.

For the survey, all health professionals involved with the intervention arm (n=9) and all service users in the intervention arm (n=30) will be included. The aim is to gain stakeholder views on the intervention.

For the qualitative interviews, a convenience sample of 12 participants will be selected. This will include all nurses, GP's and pharmacists in the intervention arm, as well as a purposive sample of 3 patients. The patients will be selected based on the most positive and most negative responses in the survey. The aim is to gain stakeholder views on the intervention and to supplement and illustrate the RCT data.

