2.2 Trial Design

Phase 1

- Validity testing: content validity index (CVI), cognitive interviews, construct validity testing
- Feasibility trial
- Reliability testing (inter-rater reliability)

Phase 2

[figure not shown]
- Randomised controlled trial (cluster group randomization by GP practice, intervention arm (ADRe Profile implementation), control arm (standard of care))

Phase 3

- Interviews and survey with participants of phase 2

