The Consultees will have as much time as they need to consider the study and will have the opportunity to ask the practice nurse/or the researcher questions before giving their advice regarding the inclusion of the person lacking capacity.

The practice nurse/researcher will obtain written confirmation that the Consultee has provided consent by means of a Consultee dated signature on the Consultee Declaration Form, and dated signature of the person who presented and obtained the declaration.

The original signed form will be retained in the participant's medical records, a copy will be provided to the researcher for the ADRe Study site file in the ADRe office, and copies will be offered to the participant or his/her family and the consultee.

Parts of the study involve single contact with researcher, so there is little scope for non-compliance (content validity index, cognitive interviews, construct validity, survey, interviews). The feasibility trial (n=20) and the intervention arm of the trial (n=30) involve 3 and 5 points of contact (in person or virtual), respectively. If the participant becomes too unwell to respond to ADRe, and there is no consultee available, they will not be asked to complete a 2nd ADRe. However, unless informed otherwise, we shall retain collected data and collect information from patients' notes as originally planned.

4. Study Procedures

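### The 90% power in Section 7.4 allows for clustering only through a design effect; with three practices per arm, a two-sided 5% t-test on practice proportions has about 67-70% power.

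*Combined protocol and SAP*

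**What the plan says.** Section 2.2 describes Phase 2 as a randomised trial with "cluster group randomization by GP practice". Section 7.4, repeated in 3.1, sets out the sample size. In an earlier single-arm study "17/19 (89%) had improvement in at least 1 clinical problem when ADRe Profiles for polypharmacy were used". The plan assumes 9/19 (47%) would improve without the intervention, "necessitating an effective sample of 40 patients (20 in each arm), with 5% significance and 90% power". It then applies a reported ICC of 0.02 "and a design effect of 1.18, to achieve an effective sample size of 40, we need an actual sample size of 48". Six practices of 10 patients give 60, which leaves 48 after 20% loss. Section 7.4 also puts 30 service users in the intervention arm. Section 4.3 says that the sample size takes the cluster design into account.

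On analysis, Section 7.1 says before-after differences will be calculated for "problems addressed, prescription regimens, NHS use, and compared, adjusting for site". Section 7.5 says GP practice and other factors will be "accounted for in exploratory bivariate and multivariate regression analyses". It adds: "The prevalence of problems on the before and after profiles will be compared with two by two contingency tables", using McNemar's test.

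**The concern.** A design effect inflates the variance of the comparison. It does not allow for the between-practice variation having to be estimated, here from six practices. Thirty intervention patients at 10 per practice imply three practices per arm, so a practice-level comparison has 6 - 2 = 4 degrees of freedom. Its two-sided 5% critical value is 2.776 rather than 1.96.

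The plan also attaches no analysis to its power figure. The powered outcome is improvement in at least one clinical problem, compared between arms. McNemar's test compares before with after. The regressions are exploratory, and adjustment for site is not specified further. Section 7.4 does not say whether the 5% is one- or two-sided.

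A reader of a null result would take the chance of having missed the assumed difference to be 10%. Under a two-sided practice-level t-test it is about 30-33%.

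**Working it through.** **Inputs (Section 7.4 unless stated).** p1 = 17/19 = 0.8947; p2 = 9/19 = 0.4737; difference 0.4211; ICC 0.02; six practices of 10; 48 evaluable, so m = 8 per practice. Randomisation by practice is from 2.2. The 3 v 3 split is inferred from 30 intervention patients at 10 per practice. Two-sided 5% and equal practice sizes are assumptions.

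**1. The plan's own figures.** The unpooled two-sided normal formula gives

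n per arm = [p1(1-p1) + p2(1-p2)] × (1.960 + 1.282)² / (p1-p2)² = (0.0942 + 0.2493) × 10.51 / 0.1773 = 20.4.

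This matches the stated 20. A one-sided pooled formula gives 18.9, so it fits 20 too and the sidedness cannot be inferred. The rest follows: 1 + 9 × 0.02 = 1.18; 40 × 1.18 = 47.2, stated as 48; 60 × 0.8 = 48.

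**2. Same inputs, t-test on practice proportions, 4 df.**

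SE² = [p1(1-p1) + p2(1-p2)] × [1 + (m-1) × ICC] / (3m)

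At m = 8: 0.3435 × 1.14 / 24 = 0.01632, so SE = 0.1277 and the noncentrality is 0.4211 / 0.1277 = 3.30. With critical value 2.776, the noncentral t gives 69.7%. The normal approximation behind this is rough for counts out of 8, so the same test was also simulated with beta-binomial counts (200,000 runs). Its two-sided type I error was 4.5-5.0%.

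| Scenario | Noncentral t | Simulation |
|---|---|---|
| 48 evaluable, ICC 0.02, two-sided | 69.7% | 66.6% |
| 60 evaluable, ICC 0.02, two-sided | 77.2% | 74.1% |
| 48 evaluable, ICC 0.02, one-sided | 85.2% | 83.1% |
| 60 evaluable, ICC 0.02, one-sided | 90.3% | 88.6% |
| 48 evaluable, ICC 0, two-sided | 74.9% | 72.0% |
| 48 evaluable, ICC 0.05 (assumed), two-sided | 62.7% | 60.3% |
| 48 evaluable, ICC 0.10 (assumed), two-sided | 53.5% | 52.1% |

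Retaining each of the 60 patients with probability 0.8, so that practice sizes become unequal, gives 67.7% by simulation (two-sided, ICC 0.02). Even an ICC of zero does not restore 90% at 48 evaluable, so the shortfall comes mainly from the number of practices.

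**3. Patient-level tests, two-sided, 48 evaluable, ICC 0.02 (simulated).**
- Chi-square ignoring practice: power 90.4%; type I error 7.8% at a common rate of 0.474 and 7.0% at 0.684.
- Chi-square divided by 1 + 7 × 0.02 = 1.14: power 88.4%; type I error 4.5% and 5.5% at those rates, if the ICC really is 0.02.

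**4. Sensitivity to the control rate (assumed values), two-sided, 48 evaluable, ICC 0.02.** Control 8/19: 76-80%. Control 10/19: 57-59%.

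**5. Precision.** The expected 95% half-width with t(4) at 48 evaluable is 2.776 × 0.1277 = 0.355 by formula and 0.330 by simulation, that is, 33-35 percentage points.

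**The case against.** The strongest reply is that the t-test on practice proportions is not in the protocol, and power is undefined until a test is named. That is right, and the figure moves with the method. A t(4) test with the practice variance component held non-negative has 59.5% power. An exact permutation test of 3 v 3 has C(6,3) = 20 allocations, so its smallest two-sided p-value is 2/20 = 0.10 and it can never reach 5%. The 67-70% is therefore a conditional illustration. This supports naming the analysis; it does not rescue an unconditional 90%.

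Second, on the plan's own terms, with the ICC taken as 0.02, a patient-level test with that ICC fixed gives 88.4% power and acceptable type I error. That also stands, but its validity depends on 0.02 being correct, and the plan does not propose that test. Nor does the plan propose ignoring practice, so the 7-8% type I error describes one route to 90%, not a stated intention.

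Third, one-sided testing would narrow the gap: 83-85% at 48 and 89-90% if nobody is lost. If that was meant, 7.4 should say so.

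Fourth, the relevant objective in 2.1 is exploratory and the remedy changes nothing in conduct. This limits the consequences. Even so, 2.1 lists Phase 2 clinical impact among the primary endpoints and 7.4 makes a formal power claim.

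Finally, the upper end of 67-70% is an approximation. The simulated value, about 67%, is the better guide.

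**Conclusion.** The concern holds. The arithmetic in 7.4 is sound as a patient-level calculation with a design effect, but its 90% does not carry over to a comparison of three practices with three. At 89% v 47% and ICC 0.02, with equal practice sizes and a two-sided 5% t-test on practice proportions, power falls short of the stated figure by 20 to 23 percentage points at 48 evaluable patients and by 13 to 16 points if all 60 are retained. No analysis named in 7.1 or 7.5 both respects randomisation by practice and delivers 90% two-sided.

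The missing allowance for few practices and the missing between-arm test are firm. The exact power depends on the assumed sidedness, the choice of test and the inferred 3 v 3 split. This should be fixed.

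**What to change.** In 3.1 and 7.4, state whether the 5% is one- or two-sided and replace the unconditional 90%. If two-sided, for example:

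> For 89% v 47% and an ICC of 0.02, a two-sided 5% t-test on practice-level proportions (3 v 3 practices, 4 df, equal practice sizes) has about 67-70% power with 48 evaluable patients and 74-77% if all 60 are retained. The 90% figure comes from a patient-level calculation inflated by a design effect, which does not allow for the small number of practices.

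If one-sided is intended, say so and give 83-85% at 48. Power at ICC 0.05 and 0.10 may be added, labelled as assumptions.

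In 7.5, name the between-arm analysis of improvement in at least one problem, and report it with a 95% confidence interval that accounts for randomisation by practice and for the small number of practices. A t(4) interval on practice proportions is one option. If another method is chosen, quote the power of that method instead.

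The cost is wording in three sections, a less favourable stated power and a wider reported interval. No patients, practices or visits are added.
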